### HYPOTHESIS

The repellent samples are expected to provide 8 hours of personal protection from *Culex quinquefasciatus* mosquitoes, a West Nile virus vectors, in the laboratory.

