### OBJECTIVE

The objective of the study is to determine the mean protection time from bites provided by the test articles under laboratory conditions to confirm the hypothesis. Therefore ICR will conduct a laboratory study to assess repellency of these test articles against *Culex quinquefasciatus* mosquitoes.

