While there is obviously an economic incentive to the sponsor of the study to offer a new insect repellent alternative to consumers, such products must offer a recognized benefit to consumers or they will simply not be purchased or used. It is important to bring new insect repellent products to market so that consumers have alternatives that they find personally acceptable and convenient to use to protect themselves and family members from irritating and potential disease-carrying insect bites. New products, such as the proposed test samples, have been formulated to provide protection from insect bites in combination with other benefits that promote consumer acceptance and use of the product (i.e., convenience of product form or method of application, fragrance preferences, preference for, or avoidance of, a specific active ingredient, etc.).

ICR prefers to evaluate repellency based on protection from bites rather than landings while conducting laboratory studies. Disease transmitted by laboratory raised mosquitoes that have not been exposed to any arboviruses is not possible. Therefore there is no risk of disease transmission to any of the test subjects.

In this study efficacy is defined as the Protection Time (PT). The PT is the time interval between the application of the repellent and the First Confirmed Bite (FCB). A bite is defined as the ingestion of blood by a mosquito while it is on a repellent-treated area of skin, as evidenced by an enlarged, blood filled abdomen of the mosquito. The FCB is a bite which is followed by another bite within 30 minutes.

This study may be submitted to EPA to support an insect repellent label claim. The efficacy study will test the repellent formulations in controlled laboratory conditions, exposing test subjects to only disease-free mosquitoes.

According to the EPA OPPTS Guideline No. 810.3700 "Product Performance of Skin-Applied Repellents of Insect and Other Arthropods", there exists no alternative to evaluating topical repellents on human subjects; therefore, field or laboratory testing of repellents is necessary.

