### *Testing*

The aggressiveness of the caged mosquitoes during the test day will be determined from the landing rate on the control's arm before each test exposure. Once the landing rate has been confirmed (5 landings in 60 seconds) the counts will cease. The landing rate verification will be conducted before each exposure of the treated test subjects. If fewer than the required number of mosquitoes land in 60 seconds, a new group of 100 mosquitoes will be released into all of the cages.

The study director or technician will assist the test subjects in inserting their arms into the test cages, taking care not to rub them on the cloth sleeve. The test subjects will expose their treated forearms to the mosquitoes in these test cages for 5 minutes. The subjects will then remove their arms from the cages with assistance from an ICR staff. Exposures to the mosquitoes will be repeated every 30 minutes until the formulation on any given forearm is determined to be no longer effective or until 8 hours have elapsed, whichever occurs first.

The test data to be recorded will be bites (blood is ingested, as evidenced by abdominal swelling and color change). Test data will be recorded on a Repellency Test Data Sheet.

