### *Criteria for Test End Point*

Efficacy will be evaluated by intermittent exposure of the test subjects' arms. The treated test subjects will expose their treated arms to the caged mosquitoes for 5 minutes at approximately 30 minute intervals. The test subjects will expose treated arms until the FCB (when two bites occur on the same arm in the same exposure period, or one bite occurs in each of two consecutive exposure periods, the first bite being the confirmed bite) or until 8 hours have elapsed, whichever occurs first. For the purposes of this test, a bite is defined as a mosquito penetrating the skin with its proboscis and taking sufficient blood to cause its abdomen to swell. When the two bites have occurred as noted above, the test will terminate on that arm.

When the testing is terminated for an arm, test subjects will then roll down their sleeves to cover such discontinued arms. The test will be terminated on a treated arm when a bite is followed by one additional bite (the initial bite and one confirming bite). If the bites do not occur within the specified time, the number of bites required will begin anew.

Once a confirmed bite occurs, the test subjects will stop exposing that arm to mosquitoes. They will then be able to remove the bandages and tape, scratch and wash that arm. If they want to, they can use rubbing alcohol to help stop the itching from the bites they may have received. Caladryl® or Calamine® lotion may also be used.

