### **DATA ANALYSIS:**

The purpose of this study is to examine the effective duration of an insect repellent. Ideally, it is expected that there will be no significant breakdown in efficacy of the product over a 8 hour interval. Given the small sample size ( $N = 10$ ) and the dichotomous nature of the data (effective vs. non-effective), nonparametric statistics will be used to analyze the data. Data will be analyzed using SPSS for Windows version 12.

Subjects will be evaluated each half hour over the 8 hour window of the study to determine whether or not the product continued to prevent insect bites. For each 30 minute assessment interval, the proportion of subjects not having insect bites will be identified. A basic degradation curve can then be plotted. These data will then be subjected to a Cochran Q test, which is particularly useful for measuring changes in frequencies (proportions) across time. A significant effect would indicate that there was a systematic degradation in the product's efficacy over the 8 hour testing interval. If such an effect is found with the Q test, then a series of 2 (baseline vs. assessment interval) X 2 (protected vs. non-protected) cross-tabulations will be created and the resulting proportions will be analyzed using a Fischer's Exact Test (employing a 1-tailed alpha level) to determine the specific time point at which efficacy became significantly impaired.

Data also to be collected from subjects will be the length of time before a significant number of bites were noted. These data will be aggregated and basic descriptive statistics determined (e.g., mean, standard deviation, confidence intervals). If this distribution is non-normal, appropriate transformations will be applied and statistics recalculated. In the case of negative skewness (which is expected), the data will be reflected and a logarithmic transformation will be employed. In the case of significantly skewed distributions, the median will be used as the measure of central tendency. Confidence intervals will be calculated on the basis of percentile ranks rather than standardized scores.

QAU AND DATA ARCHIVING

Good Laboratory Practices, as outlined in 40 CFR §160 will be followed throughout the study. The QAU representative will observe and write phase report(s) for this study. All data will be archived.

SCHEDULE OF EVENTS

DATE	PROCEDURE
Time Zero	Test Conducted
At End of Test	Verbal Report
After The Laboratory Test Conduct	Written Report

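### Mean, SD and reflect-and-log summaries ignore the 8-hour cut-off, so the mean named in the objective cannot confirm 8-hour protection

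*Protocol*

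**What the plan says.** HYPOTHESIS states: "The repellent samples are expected to provide 8 hours of personal protection". OBJECTIVE sets out to "determine the mean protection time from bites provided by the test articles under laboratory conditions to confirm the hypothesis". Under STUDY RATIONALE, protection time (PT) runs from treatment to the first confirmed bite (FCB), and earlier picaridin tests are said to have lasted up to and past 8 hours.

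Under Testing, exposures are repeated every 30 minutes until the product on that arm is "determined to be no longer effective or until 8 hours have elapsed, whichever occurs first". Criteria for Test End Point gives the same stop: "or until 8 hours have elapsed, whichever occurs first".

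DATA ANALYSIS plans two things. The first is the proportion of unbitten subjects at each 30-minute assessment, with a degradation curve and tests. The second is a summary of times by mean, SD and confidence intervals. For the times it adds: "In the case of negative skewness (which is expected), the data will be reflected and a logarithmic transformation will be employed". It then moves to the median if the skew is significant, and ends: "Confidence intervals will be calculated on the basis of percentile ranks rather than standardized scores". It gives no rule for an arm that reaches 8 h without an FCB.

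**The concern.** An arm without an FCB at 8 h is right-censored. The hypothesis and the cited experience make such arms likely, so the negative skew that the protocol expects is largely the heap of values at the cut-off. A transformation changes the spacing between distinct values. It cannot recover what lies beyond the cut-off or separate tied values.

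At stake is the quantity that the OBJECTIVE names, in a study meant to support a label claim. A mean of times that stop at 8 h drops below 8 h as soon as one arm fails before the last exposure, however long the other arms would have lasted. It is therefore most wrong where the product performs as hoped.

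**Working it through.** The plan gives no figure of its own for this bias, so there is none to reproduce.

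**Inputs.** The cut-off is 8 h and the spacing 30 minutes (Testing). There are 10 treated subjects as planned, or 12 arms per product (sample-size rationale; Experimental Design). The SD of 2.0 h is the value in the sample-size rationale, borrowed here as an assumption. The true means, the normal shape and a second SD of 3.3 h are also assumptions. Survivors are entered as 8.0 h, which is an inference. The times summarised in DATA ANALYSIS are taken to be PT.

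**Step 1: mean of capped times, without the grid.** For T normal with mean m and SD s, let z = (8 − m)/s. Then E[min(T, 8)] = 8 − [s·φ(z) + (8 − m)·Φ(z)].

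- m = 8: 8 − 2 × 0.3989 = 7.20 h
- m = 9: 8 − (2 × 0.3521 − 1 × 0.3085) = 7.60 h
- m = 10: 8 − (2 × 0.2420 − 2 × 0.1587) = 7.83 h

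**Step 2: the same on the 30-minute grid, by simulation (40,000 runs).** Coverage is that of a nominal 95% t-interval for the true mean.

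| True mean, SD (h) | Recorded mean, n=10 | Bias | Recorded SD, n=12 | Coverage n=10 | Coverage n=12 |
|---|---|---|---|---|---|
| 6, 2 | 6.04 | +0.04 | 1.65 | 94% | 94% |
| 8, 2 | 7.33 | −0.67 | 1.03 | 67% | 51% |
| 8, 3.3 | 6.82 | −1.18 | 1.72 | 61% | 44% |
| 9, 2 | 7.68 | −1.32 | 0.66 | 0% | 0% |
| 10, 2 | 7.87 | −2.13 | 0.34 | 0% | 0% |

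Lognormal times give nearly the same bias.

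**Step 3: does reflect-and-log help?** Take nine arms at 8 h and one at 6 h. The skewness is −2.67, and the skewness of log(9 − x) is +2.67. Reflection flips the sign and the log removes nothing, because a two-valued sample stays two-valued. In the simulation at true mean 8 h, SD 2 h and n=10, the back-transformed estimate (constant 9) is 7.54 h with 54% coverage of the true mean. At 10 h coverage is still 0%.

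**Step 4: one data set, several answers.** Take seven arms at 8 h and failures at 5, 6 and 7 h.

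- Mean: (7 × 8 + 18)/10 = 7.40 h.
- Reflected-log with constant 9: 9 − (4 × 3 × 2)^(1/10) = 9 − 1.37 = 7.63 h.
- Median: 8 h, properly read as 8 h or more.

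The percentile-rank sentence can be read in two ways. As a rank-based interval for the median, ranks 2 and 9 of 10 give 6 h to 8 h or more, with coverage 1 − 2 × (1 + 10)/1024 = 97.9%. As sample percentiles, it gives about 5.2 to 8 h, which describes the spread of the arms.

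**Step 5: the boundary case.** If every arm reaches 8 h, the mean is 8, the SD is 0 and the interval shrinks to a point. The exact two-sided 95% lower bound for the proportion protected still carries information: 0.025^(1/10) = 0.69 for 10/10 and 0.025^(1/12) = 0.74 for 12/12.

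**The case against.** A reader might infer that the study as a whole cannot confirm 8-hour protection. The documents do not support that. DATA ANALYSIS plans the proportion unbitten at every assessment, and at 8 h this needs no censoring method if no arm leaves early. It also names the median under significant skew, and the cut-off barely affects a median when fewer than half the arms fail. At true mean 10 h, SD 2 h and n=10, the sample median averages 8.00 h and its lower 97.9% limit is 8 h in 72% of runs.

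A reader might also take the coverage figures as a verdict on the protocol's own interval. They are for a t-interval, whereas the protocol names percentile ranks, at least for skewed data. A rank-based interval for a median is a valid method: at true mean 8 h it covers in 99% of runs (n=10). At 9 and 10 h its lower limit holds, and only an upper limit read literally as 8 h misses.

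Nor does the protocol say that survivors are coded as 8 h. That part remains an inference, but a mean and a reflection need a number for every arm, and leaving survivors out would push the mean lower still.

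The reflection constant and the exact interval formula may properly wait for an analysis plan, and nothing here rests on them.

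These points narrow the finding without removing it. The median fallback has no threshold for significant skew. It competes with the transformation rule for the same expected negative skew. It does not estimate the mean that the OBJECTIVE names.

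**Conclusion.** The point holds for the mean, the SD and the transformed mean: as planned, they make no allowance for censoring at 8 h and cannot confirm 8-hour protection. With normal times, SD 2 h, ten arms, the 30-minute grid and survivors entered as 8 h, the recorded mean is too low by about 0.7, 1.3 and 2.1 h at true means of 8, 9 and 10 h. If protection is well short of 8 h (true mean 6 h), the bias is negligible. The size depends on these assumptions. The direction, and the ceiling of 8 h, follow from the stopping rule once survivors are given that value. The planned 8-hour proportion and median fallback are partial safeguards. The wording should be corrected before testing, because the affected quantity is the stated objective.

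**What to change.** Rewrite the last paragraph of DATA ANALYSIS:

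- Analyse time to FCB for each product by Kaplan-Meier, censoring arms without an FCB at 8 h or at withdrawal.
- Report the median with a 95% CI, allowing limits of *8 h or more* or *not reached*.
- Report the proportion protected at 8 h with an exact (Clopper-Pearson) CI.
- Label any mean as restricted to 8 h.
- Delete the reflect-and-log step and the choices driven by observed skewness, and replace the percentile-rank sentence with the named intervals.

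Change the OBJECTIVE from mean protection time to the median and the 8-hour proportion. The cost is protocol wording only, since the data already planned are enough. The downside is that a single mean is no longer the headline figure.

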## RAW DATA COLLECTION SHEET

SPONSOR: 059      DATE:      START TIME:

S D/TECH: [name]      SPECIES: *C. quinquefasciatus*      FORMULATION APPLIED BY: [name]

COMP	SUBJ		SUBJ		CONTROL INITIALS: _____	
	RIGHT	LEFT	RIGHT	LEFT	LAND	TIME
TIME	BITE	BITE	BITE	BITE		
0.5						
1.0						
1.5						
2.0						
2.5						
3.0						
3.5						
4.0						
4.5						
5.0						
5.5						
6.0						
6.5						
7.0						
7.5						
8.0						
Fail Time						

Signatures of Study Associates  
Recording data on this sheet/date:

\_\_\_\_\_  
\_\_\_\_\_  
\_\_\_\_\_

Study Director's Signature/Date \_\_\_\_\_

Test Subject's Initials/Date \_\_\_\_\_

## Repellent Measurements—Arm

SUBJECT: \_\_\_\_\_

DATE: \_\_\_\_\_

### LEFT ARM

LOWER ARM = \_\_\_\_\_

AVG = \_\_\_\_\_  $\frac{250 \text{ cm}}{2}$  = \_\_\_\_\_

UPPER ARM = \_\_\_\_\_

CENTER POINT = DISTANCE FROM LARGE TO SMALL CIRCUMFERENCE  $\frac{\text{cm.}}{2}$  \_\_\_\_\_

DISTANCE FROM CENTER POINT TO TIP OF LITTLE FINGER \_\_\_\_\_

DISTANCE FROM EITHER SIDE OF CENTER POINT \_\_\_\_\_

### RIGHT ARM

LOWER ARM = \_\_\_\_\_

AVG = \_\_\_\_\_  $\frac{250 \text{ cm}}{2}$  = \_\_\_\_\_

UPPER ARM = \_\_\_\_\_

CENTER POINT = DISTANCE FROM LARGE TO SMALL CIRCUMFERENCE  $\frac{\text{cm.}}{2}$  \_\_\_\_\_

DISTANCE FROM CENTER POINT TO TIP OF LITTLE FINGER \_\_\_\_\_

DISTANCE FROM EITHER SIDE OF CENTER POINT \_\_\_\_\_

DATA TRANSFER VERIFIED BY: \_\_\_\_\_ DATE: \_\_\_\_\_

**Additional Materials:**

**Site Application Letter**  
**Resumes/CVs of investigator and sub-investigators**  
**Material Safety Data Sheets for Test Materials**  
**Indemnification Form**  
**Investigator Attestation**  
**Investigator Conflict of Interest Declaration**  
**Memo regarding ongoing training for investigators and staff**

# SITE APPLICATION LETTER

Date 7-25, 2007

Chairman  
Essex Institutional Review Board, Inc.  
[name]  
Lebanon, NJ 08833-2162

In connection with the [Sponsor] Avon Products, Incorporated clinical research project, entitled:  
[Protocol Title] EVALUATION OF THE EFFICACY OF PERSONAL REPELLENTS AGAINST MOSQUITOES  
IN THE LABORATORY

and [Protocol number] G0590607001A117

application is being made to the Essex Institutional Review Board for review under the provisions of 21 CFR 50, 21 CFR 56, 45 CFR 46, and 40 CRF 26.

The following information will assist the Essex IRB review of your request. All questions must be answered completely.

**You must transmit this letter for each site requesting review and approval.**

- A Form 1572 (if applicable to this study) listing each research site is attached.  
 A Form 1572 is not applicable to this study. A copy of the Investigator Attestation Form is attached.  
 A copy of a valid IND, when one is required. A copy of the Form 1572 or a copy of the Investigator Attestation Form is attached.  
 For device study, attach IDE letter from the FDA or statement supporting non-significant risks or why exempt from IDE requirements under 21 CFR 812.2 or otherwise exempt. A copy of the Investigator Attestation Form is attached.

# SITE APPLICATION LETTER

2b. A site should ensure that adequate medical care is provided to subjects for any adverse events. Does the site have a policy and provisions for handling adverse reactions, including abnormal lab results related to the trial?

Yes

No (Please explain) \_\_\_\_\_

3. Can the principal investigator be reached 24-hours a day? (NOTE: Answering machines not acceptable)

Yes

No (Please explain) \_\_\_\_\_

4. **Hospital to be used in an emergency:**

Distance from site: 10 miles

Name: St. Agnes Hospital

Address: [name]  
Baltimore, Md. 21229

[contact]

Is this hospital equipped to handle adverse reactions?

Yes

No

5. The research site listed in question 2a is [check all boxes that apply]:

a)  Independent private practice(s).

b)  Private practice(s) located within a hospital or teaching institution.

c)  Hospital(s) or teaching institution(s) **without** a local IRB.

d)  Other [specify]: Contract Testing Laboratory

[if only 5a, 5b, 5c and/or 5d are selected, skip to question 7]

e)  Hospital(s) or teaching institution(s) with a local IRB.

6. The local IRB could have jurisdiction over this study.

Yes [if yes, attach local IRB waiver letter]  No

# SITE APPLICATION LETTER

7. The local IRB has restrictions on independent IRB approval of this study for the listed site.  Yes [if yes, attach listing of restrictions]  No

8. Has this protocol been submitted to, reviewed by, disapproved, terminated and/or withdrawn from another IRB?  Yes [if yes, attach IRB findings]  No

9. Is there a local community attitude that could impact on the manner in which your study will be conducted?  Yes [if yes, attach listing of attitudes]  No

10. Please provide the names of the sub-investigators in this study. If none, please write "NONE". (This includes any individual member of the clinical trial team designated and supervised by the investigator at a trial site to perform critical trial-related procedures and/or to make important trial-related decisions.) (If necessary, please attach an addendum providing the names of the sub-investigators)

[name], [name], [name], and [name]

CVs on file at Essex IRB

NOTE: These names must be listed on the 1572 form [Box 6], if required by this study type.

**Include resume(s) and current license(s)/certification.**

11. Do you personally attend to research participants at this site?  Yes  No

If "No", list the names of those who attend the participants: \_\_\_\_\_

**Include resume(s) and current license(s)/certification.**

12. In your absence, research-related medical emergencies are handled by which healthcare giver?

[name] and [name] are both CPR and First Aid Trained and certified

**Include resume(s) and current license(s)/certification.**

13. a. How will you identify and recruit potential subjects? \_\_\_\_\_

From a list of past study participants

b. Will there be any bonus payment for recruiting participants?  Yes  No

If yes, please explain and submit amounts: \_\_\_\_\_

# SITE APPLICATION LETTER

---

14. Will subjects be eligible to participate in any additional studies during this trial?

Yes (Please explain)  No

---

15. Please provide information about the planned methods for obtaining informed consent.

I. When will the consent process take place? Before the test begins

II. Where will the consent process take place? At the test site

III. How will you verify whether the subject understands or has the capacity to comprehend what has been explained the consent process?

Subjects will have time to ask questions, and decline to participate if they choose. The principal investigator will ask if the informed consent document is understood, and if subjects will sign to verify comprehension and acceptance.

IV. Will you provide the opportunity for the prospective subjects to consider whether or not to participate?  Yes  No (Please explain)

V. For studies of greater than one year duration, will you be reviewing the consent form again with the subject?  Yes  No (Please explain)

ICR's studies with human subjects do not last that long.

---

16. Please list the individuals other than the principal investigator and sub-investigator(s) as requested below. If none, please write "NONE". Include resume(s) and current license(s)/certification.

a. Individual(s) who will administer the consent form at this site:

.None

b. Individual(s) involved with this study (include responsibility):

.None

---

17. a. Will a non-English consent form be required for your study population?  Yes  No (skip to Q. 18).

b. If so, what language(s)? \_\_\_\_\_

Would you like Essex IRB to contract for this service?  Yes  No

If "Yes", consult the Essex IRB Fee Schedule for estimated fees.

If "No", consult the "submission guidelines" for translation certification required.

---

## SITE APPLICATION LETTER

18. Has the Food and Drug Administration inspected this site and/or investigators?

Yes (Continue with next question)

No (Skip to Q. 19)

If inspected, was a Form 483 issued at the end of the inspection?

Yes (if yes, attach copy of the Form 483 & related correspondence for Board review)

No (if no, attach any related correspondence with the FDA for verification)

Was a Warning Letter subsequently issued?

Yes (If yes, attach copy(ies) of all correspondence for Board review)

No

19. Has the FDA, OHRP or any regulatory agency, a Sponsor, or an IRB ever terminated a study at this site?

Yes (If yes, attach explanation for Board review)

No

20. Does this site have established, written standard operating procedures?

Yes

No

21. a. Does this site have ongoing training for investigators and staff in clinical research procedures in addition to any professional licenses and/or certifications?

Yes

No

If yes, please provide a memo stating the type of training (i.e. ACRP, NIH, in-house training, seminars, literature, staff meetings, etc.). Provide any certificates, letters, etc. if applicable.

b. Does anyone plan to become certified?

Yes

No

c. May we assist anyone in obtaining certification?

Yes

No

22. We need to know if you or anyone involved with this research has any financial or nonfinancial conflict of interest (COI) that could compromise or lessen the safety and welfare of subjects who enroll in the study. Please complete the separate Investigator Conflict of Interest Form and submit with this form.

The threshold amount is \$50,000 or more equity in the sponsor. If you qualify for a COI, please attach a separate sheet to describe how it will be managed and who will have the authority to impose those measures, how subjects and others will be informed and whether you have a COI Committee or equivalent backed by policies and procedures.

[figure not shown]
